Exclusion criteria	
Patients who meet any of the following criteria are not eligible for this study:
 
 1. The patient has clinically significant non-Wolfram related CNS involvement which is judged by the investigator to be likely to interfere with the accurate administration and interpretation of protocol assessments. 2. The patient has a known defect in oxidative phosphorylation (such as a confirmed mitochondrial myopathy) 3. The patient has abnormal liver function (defined as serum transaminases more than twice the upper limit of normal for the reference laboratory) 4. The patient has a significant medical or psychiatric co-morbidity that might affect study data or confound the integrity of study results. 5. The patient has received treatment with any investigational drug within the 30 days prior to study entry. 6. The patient has received blood product transfusions within 90 days prior to screening. 7. The patient is unable to comply with the protocol, (e.g. has a clinically relevant medical condition making implementation of the protocol difficult, unstable social situation, known clinically significant psychiatric/behavioral instability, is unable to return for safety evaluations, or is otherwise unlikely to complete the study), as determined by the Investigator. 8. The patient has a known history of central apnea and/or ventilation requirements. 9. The patient has a known history of chronic obstructive pulmonary disease, pleural effusion, and/or myocardial disease.
Number of patients planned and duration of study participation	
Up to 50 patients (25 adults and 25 children) will be enrolled to provide a total of a) 46 evaluable patients who complete the study (23 adults and 23 children), based on an anticipated drop-out rate of 10%;
 
The planned duration of oral dantrolene sodium administration in this study is 6 months with an optional extension phase up to 24 month. The planned overall duration of each patient's participation in this study is 9 months. For participants who continue in the optional extension phase, the planned overall duration is up to 27 months (screening, study drug dose maximization, outcome measure evaluation, and final safety follow-up).

Treatment administered and treatment schedule	
Patients who receive study drug will undergo a run-in period (3 weeks) for dose maximization.
 
Adults

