- Final Safety Follow-Up (all patients): within 28 days (+/- 7 days) following discontinuation of study drug.

Patient eligibility will be based on a diagnosis of Wolfram syndrome. Eligibility will be confirmed during the baseline screening visit. Patients who have provided written informed consent/assent to participate in this study will undergo baseline screening procedures, which will include a review of the study entry criteria and standard laboratory tests (serum chemistry, hematology and urinalysis), genetic testing confirmation, ophthalmic examination, standardized neurological and endocrinology evaluations. When central apnea is suspected in a participant, baseline screening will include the confirmation of the absence of central apnea based on the result of most recent polysomnography. Patients who are confirmed eligible based on the results of the baseline screening assessments will be enrolled to receive study drug.

Baseline procedures will include complete physical exam, standard clinical laboratory tests (serum chemistry, liver function tests, hematology and urinalysis, bone chemistry), protocol-specific laboratory testing (e.g.), 12 lead ECG. If there are no safety concerns, patients will begin the 3-week dose maximization period of the study drug.

We will perform ECG before and 4 hours after the first dose of dantrolene sodium, then again at months 2 and 6. For participants in the optional extension phase, we will also perform ECG at months 12, 18, and 24.

All patients will undergo outcome measure evaluations at month 6. Participants in the optional extension phase undergo outcome measure evaluations at months 12, 18, and 24.

[figure not shown]
Outcome measure evaluations will include standard clinical laboratory tests (serum chemistry, haematology and urinalysis), 12-lead ECG, vision assessments, neurological examination, remaining beta cell function assessment (boost test), protocol-specific laboratory testing, and standardized functional activities of daily living tests.

A Final Safety Follow-Up visit will be conducted at 28 days (+/- 7 days) after the outcome measure evaluations to collect updated information on adverse events and concomitant medications, therapies and procedures. For patients who discontinue prior to the outcome measure evaluations, this will be conducted within 28 days (+/- 7 days) after the last dantrolene sodium administration.

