	
Administration of dantrolene sodium will be contingent upon normal results of the relevant safety laboratory tests and measures (i.e., LFTs).
 
All adverse events, safety lab results and use of concomitant medications will be monitored closely by the PI throughout the study and for 30 days following discontinuation of study medication. If any clinically significant laboratory or clinical abnormality occurs, the subjects will be monitored closely until resolution or clinically stable. Study medication will be discontinued if indicated. Progress of the trial will be determined following periodic reviews by a Data and Safety Monitoring Board (DSMB) of the safety data in all previously enrolled patients.

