Statistical Methodology	
The first aim of the statistical analysis will be to assess safety and tolerability of dantrolene sodium in this patient population. The analysis will be based on all enrolled patients and will not include any formal statistical tests. To evaluate safety, the number and percentage experiencing each adverse event will be tabulated and compared by treatment status. Adverse events will be summarized by severity and by category. Vital signs, and serum chemistries, hematology and urinalysis safety monitoring will be listed for each patient and abnormal values will be flagged. The maximum dose received by patients, duration of treatment and reasons for dose reductions or early withdrawal will be reported to assess tolerability of treatment.
 
The second aim of the statistical analysis will be to assess efficacy in terms of the secondary outcome measures of residual beta cell functions, visual acuity, and neurological function. Each variable will be quantified as a change from the baseline value. The trajectory of change for each variable will be assessed between baseline and 6-month assessments. For participants in the optional extension phase, the trajectory of change for each variable will be assessed between baseline, 6-month, 12-month, 18-month, and 24-month assessments..
 
As this is a rare disease and the trial involves only a small numbers of patients, statistical inferences will be based on estimation rather than hypothesis testing. Specifically a Bayesian approach to estimation will be used based on both non-informative and informative priors as appropriate. This type of approach has been endorsed for trials of rare diseases. Drop-outs may be replaced, such that an adequate number of evaluable patients complete the study.

Individual stopping criteria	
1. If a participant experiences more than a few but not more than 10 diarrhea stools in a single day while taking dantrolene sodium, a temporary withdrawal (48 h or longer) should be discussed with a PI. A patient with Wolfram syndrome tends to

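### The safety analysis rests on all enrolled rather than all dosed patients, so anyone enrolled but never dosed could dilute the adverse-event rates

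*Combined protocol and SAP*

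**What the plan says.** All references are to the protocol synopsis in the combined protocol and SAP.

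- **Statistical Methodology, analysis set:** "The analysis will be based on all enrolled patients", with no formal tests.
- **Statistical Methodology, safety summary:** "the number and percentage experiencing each adverse event will be tabulated and compared by treatment status". Treatment status is not defined.
- **Study methodology, enrolment:** "Patients who are confirmed eligible based on the results of the baseline screening assessments will be enrolled to receive study drug".
- **Study methodology, start of dosing.** The next paragraph lists the baseline procedures (physical examination, laboratory tests including liver function, ECG) and then says: "If there are no safety concerns, patients will begin the 3-week dose maximization period of the study drug".
- **Study methodology, laboratory condition:** "Administration of dantrolene sodium will be contingent upon normal results of the relevant safety laboratory tests and measures (i.e., LFTs".
- **Exclusion criteria.** Abnormal liver function is a reason for exclusion, and it is defined as transaminases above 2 × ULN.
- **Treatment administered and treatment schedule:** "Patients who receive study drug will undergo a run-in period (3 weeks) for dose maximization".
- **Number of patients planned.** Up to 50 patients (25 adults, 25 children), with 46 evaluable (23 and 23) at an anticipated drop-out of 10%.

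**The concern.** Safety and tolerability are the primary objective, and the percentage of patients with each adverse event is the main summary of them. Such a percentage should describe people exposed to the drug. If enrolment can happen before a condition that stops some patients from starting treatment, a denominator of all enrolled patients includes people who were never at risk from the drug. They add to the denominator and will usually add nothing to the count of treatment-emergent events, so the drug looks slightly safer than it was among those who took it. They also have no maximum dose and no treatment duration to contribute to the tolerability summaries.

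**Working it through.** **Plan's own figure.** The documents give no adverse-event rate and no number undosed. The only planning figure is 46 evaluable of 50. Overall, 50 × (1 − 0.10) = 45. By age group, 25 × 0.90 = 22.5, rounded up to 23, and 2 × 23 = 46. The figure reproduces, with the difference of one due to rounding within each group.

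**Can a patient be enrolled but not dosed?** The Study methodology text runs in this order: eligibility confirmed, enrolled, baseline procedures, then drug if there is no safety concern. On that reading, a baseline finding can stop an enrolled patient from starting. The laboratory condition is a second possible route. Both depend on wording that allows another reading (see the objection), so undosed patients are possible but not certain.

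**Size.** Let N = 50 be the number enrolled (Number of patients planned), k the number enrolled but never dosed (assumed), and x the number of dosed patients with the event (x = 10 assumed). If only dosed patients have events:

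- rate on all enrolled = x/N
- rate on dosed = x/(N − k)
- ratio of the first to the second = (N − k)/N

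| k (assumed) | All enrolled | Dosed only | Ratio | Difference |
|---|---|---|---|---|
| 0 | 10/50 = 20.0% | 10/50 = 20.0% | 1.00 | 0 |
| 1 | 10/50 = 20.0% | 10/49 = 20.4% | 0.98 | 0.4 points |
| 2 | 10/50 = 20.0% | 10/48 = 20.8% | 0.96 | 0.8 points |
| 5 | 10/50 = 20.0% | 10/45 = 22.2% | 0.90 | 2.2 points |

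The top of the range, k = 5, equals the whole anticipated drop-out (10% of 50 = 5), so it is a generous upper value.

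If results were also shown by age group (25 planned in each), one undosed patient would matter more. With 5 events assumed, the rate is 5/25 = 20.0% on enrolled, against 5/24 = 20.8% with one undosed and 5/23 = 21.7% with two.

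**Direction.** The planned table covers each adverse event, not only drug-related ones, so an undosed patient could still add an event. With k = 2 and one of those two having the event before any dose, the all-enrolled rate is 11/50 = 22.0%, which is above the 10/48 = 20.8% among dosed patients. Dilution is the likely direction, not a guaranteed one.

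**The case against.** The case for leaving the plan alone has real substance.

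- **Treatment status.** Adverse events are to be compared by this variable. If it means dosed versus undosed, the dosed column has the right denominator. This stands as a possibility. However, the term is undefined and Study methodology describes no control arm, so a reader cannot tell what is being compared.
- **Order of enrolment and baseline.** The sequence is inferred from paragraph order. Study methodology also lists baseline and confirmatory screening as a single pre-treatment period, so the safety check may in practice coincide with enrolment. This stands, and it is why the point says the text reads that way and goes no further.
- **Liver tests.** A reader might infer that patients between 1 and 2 × ULN are certain to be enrolled and then refused drug. The documents do not support that. The exclusion criterion defines abnormal as above 2 × ULN, so normal in the dosing condition may mean at or below that limit. The condition may also apply throughout treatment and not specifically to the first dose. The two statements are ambiguous together and need reconciling, but they do not prove that an undosed group exists.
- **The run-in sentence.** Its reference to patients who receive drug is introductory wording. It allows for undosed patients without establishing that there are any.
- **Safeguards.** Patient-level laboratory and vital-sign listings, maximum dose, treatment duration and reasons for withdrawal would make undosed patients visible. The study stopping criteria use counts of patients, so no denominator affects them.

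None of this supplies a safety population based on exposure, which is the remaining gap.

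**Conclusion.** The point holds in a limited form, and its severity is minor. The stated safety set is all enrolled patients, the text permits enrolment without dosing, and no set of dosed patients is defined. Any such patient could dilute the adverse-event percentages, by a factor of (N − k)/N.

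For an event in 10 patients, the shift is 0.4 to 0.8 percentage points with one or two of 50 undosed, 2.2 points with five, and zero with none. This rests on an assumed number undosed, an assumed event count, and no pre-dose events among the undosed.

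A reader might infer two stronger claims, and neither is supported. The first is that every adverse-event rate is biased downward. That fails if treatment status separates dosed from undosed patients, and pre-dose events could push a rate the other way. The second is that upper confidence limits for safety are understated. The plan describes safety without formal tests and proposes no such limits.

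**What to change.** In Statistical Methodology:

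1. Define the safety population as all patients who receive at least one dose of dantrolene sodium.
2. Use it as the denominator for adverse-event percentages, and for any laboratory and tolerability percentages.
3. List patients who were enrolled but never dosed separately, with reasons, and report any pre-dose events apart from the main table.
4. State what treatment status means and which groups it compares.

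Separately, the sponsor should reconcile the liver definition in the Exclusion criteria with the normal-results condition in Study methodology, so that it is clear who can be enrolled without starting drug.

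The cost is a few sentences, with no new data collection and no change in sample size. The one downside is that reported rates may look slightly less favourable if any enrolled patients go undosed.

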Study endpoints	
The Primary Endpoint of this study is:
 
 • To assess the safety and tolerability of dantrolene sodium administered orally up to 100 mg b.i.d. (adults) and up to 2 mg/kg b.i.d. (pediatric patients, up to 50 kg) for 6 months with an optional extension phase up to 24 months in patients with Wolfram syndrome. • Safety will be assessed by adverse events (by type and severity) and changes in clinical laboratory testing (including liver function tests). • This will be assessed by monitoring of serum chemistry including liver function tests and ammonia. • Safety will be also assessed by complete physical exam (PE), vital signs (vs)/weight (wt) at each visit 
The Secondary Endpoints include:
 
 • Determine the effect of dantrolene sodium on remaining beta cell functions using a mixed-meal tolerance test and monitoring base-line C-peptide levels, blood glucose levels, proinsulin/C-peptide ratios, hemoglobin A1c levels, and urine glucose levels. • To determine the efficacy of dantrolene sodium on visual acuity (LogMar scores) • To determine the efficacy of dantrolene dosicum on visual functions using Visual Functioning Questionnaire – 25. • To evaluate the efficacy of dantrolene sodium on neurological functions using the Wolfram Unified Rating Scale (WURS) and standard neurological assessments.
Inclusion criteria	
Patients must meet all of the following criteria to be eligible for enrolment:
 
 1. The patient has a definitive diagnosis of Wolfram syndrome, as determined by the following: 
 a. Documented functionally relevant recessive mutations on both alleles of the WFS1 gene or dominant mutation on one allele of the WFS1 gene based on historical test results (if available) or from a qualified laboratory at screening. 2. The patient is at least 5 years of age (biological age) at the time of written informed consent. 3. The patient, patient's parent(s), or legally authorized guardian(s) must have voluntarily signed an Institutional Review Board/Independent Ethics Committee-approved

	
informed consent form after all relevant aspects of the study have been explained and discussed with the patient. The guardians' consent and patient's assent, as relevant, must be obtained.

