	
Up to 25 mg once daily for seven days as prescribed by the physician, then Up to 25 mg b.i.d. for seven days Up to 50 mg b.i.d. for seven days Up to 100 mg b.i.d.
 
Pediatric Patients (a patient with an age < 18 years) up to 50 kg Up to 0.5 mg/kg once daily for seven days as prescribed by the physician, then Up to 0.5 mg/kg b.i.d. for seven days Up to 1 mg/kg b.i.d. for seven days Up to 2 mg/kg b.i.d.
 
No dose changes if weight change is within $\pm 3\%$ of the original dosing weight.
 
Dantrolene sodium for oral use will be provided by the Washington University's clinical trials pharmacy

Study duration	The duration of this study will be approximately 9 months. For participants who continue in the optional extension phase, the duration of the study is up to 27 months.
Study methodology	
This is a single center, dose-escalation study designed to evaluate the safety, and tolerability of maximal dose level of dantrolene sodium administered orally over 6 months with an optional extension phase up to 24 months in patients with Wolfram syndrome.
 
The study will have 'x' periods as follows:
 
 Baseline and confirmatory screening (all patients): within 56 days prior to treatment. Dose maximization period (weeks 0-3 for each patient). Treatment period (weeks 1-) for all patients. Week 0 through week 3 (+/- 2 days): dose escalation up to the maximum recommended. Assessments for safety at months 1 (+/- 2 days), 2 (+/- 7 days), 4 (+/- 7 days), and 6 (+/- 7 days); and clinical examination, including ophthalmic, neurologic, endocrine, and laboratory assessments at months 0 and 6 (+/- 7 days). For participants who continue in the optional extension phase, additional assessments for safety at months 12 (+/- 7 days), 18 (+/- 7 days), and 24 (+/- 7 days); and additional clinical examinations, including ophthalmic, neurologic, endocrine, and laboratory assessments at months 12 (+/- 7 days), 18 (+/- 7 days) and 24 (+/- 7 days). Outcome measure evaluations (all patients): month 6 (+/- 7 days) after the last dantrolene sodium administration for participants who complete the study, month 24 (+/- 7 days) after the last dantrolene sodium administration for participants who complete the optional extension phase, and within 28 days (+/- 7 days) after the last dantrolene sodium

administration for patients who discontinue prior to the end of the study.

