	
have diarrhea due to autonomic dysfunction. Thus, the temporary withdrawal is determined by the discretion of the PI. If a patient experiences more than 10 diarrhea stools in a single day, a temporary withdrawal (48 h or longer) should be immediately done. After the temporary withdrawal, a participant should use the previously tolerated dosing regimen.
 
2. If a participant experiences significant muscle weakness while taking dantrolene sodium, a participant should use the previously tolerated dosing regimen. Muscle weakness is examined at every study visit as part of the physical exam. Muscle weakness is assessed by the following methods.
 
 • Rise to stand from floor without using hands. If a participant cannot do this due to neurological dysfunction of Wolfram syndrome, the order in which we would like a participant to attempt is the following: From floor with hands, from a chair without using hands, from a chair with hands. • Hand grip strength using a hand dynamometer, left and right. 
If a participant cannot rise to stand with the method he/she used or a participant's total hand grip strength (sum of right- and left-hand grip strength) is decreased by more than 20% with the current dosing regimen, a patient should use the previously tolerated dosing regimen.
 
Two failures in either of these two steps would constitute stopping the drug permanently.
 
3. ALT or AST >8xUpper Limits of Normal (ULN) 4. ALT or AST >5xULN for more than 2 weeks 5. ALT or AST >3xULN and (serum total bilirubin >2xULN or international normalized ratio >1.5) 6. ALT or AST >3xULN with the appearance of fatigue, nausea, vomiting, right upper quadrant pain or tenderness, fever, rash, and/or eosinophilia (>5%)

Study stopping criteria	We define the study stopping criteria based on established adverse event criteria, the National Cancer Institute (NCI) Common Terminology Criteria for Adverse Events (CTCAE), Version 4. The study may need to be stopped if ≥2 patients on drug develop the same CTCAE Grade 3 or if 1 patient develops a CTCAE Grade 4 or higher.

FIGURE: CLINICAL TRIAL DIAGRAM

For participants who continue in the optional extension phase

**Study Visits 10,
11, and 12
Month 12, 18,
and 24**

Assessment of Clinical Outcome Measures

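### The tolerability summary shows who reduced dose and why, but not how long each patient held the maximal dose that the trial sets out to study for 6 months

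*Combined protocol and SAP*

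**What the plan says.** All places cited are in the protocol synopsis.

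- **Aim.** Study methodology says that the trial evaluates the "maximal dose level of dantrolene sodium administered orally over 6 months". The primary endpoint is worded more loosely, as safety and tolerability of drug "administered orally up to 100 mg b.i.d. (adults) and up to 2 mg/kg b.i.d. (pediatric patients, up to 50 kg) for 6 months".
- **Titration.** Dose rises through three seven-day steps before the top step: "Week 0 through week 3 (+/- 2 days): dose escalation up to the maximum recommended". Each step is a ceiling left to the prescriber; for adults the first is "Up to 25 mg once daily for seven days as prescribed by the physician".
- **Step-down.** Under Individual stopping criteria, more than 10 diarrhea stools in a day means that "a temporary withdrawal (48 h or longer) should be immediately done", after which the patient resumes the regimen tolerated before. Significant muscle weakness, checked at every study visit, also sends the patient back to that regimen. Two failures end treatment. No return to the higher dose is described.
- **Tolerability summary.** Statistical Methodology states: "The maximum dose received by patients, duration of treatment and reasons for dose reductions or early withdrawal will be reported to assess tolerability of treatment".
- **Adverse events.** In the same section, "the number and percentage experiencing each adverse event will be tabulated and compared by treatment status". On the population: "The analysis will be based on all enrolled patients and will not include any formal statistical tests". *Treatment status* is not defined.

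**The concern.** Dose changes within a patient by design, through titration, prescriber choice, temporary withdrawal and step-down. A question about the maximal dose over 6 months therefore needs two facts per patient: how long that dose was held, and what happened while it was being taken.

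Maximum dose received is reached on the first day at the top step and never falls afterwards. Duration of treatment keeps running after a step-down, and the plan does not say whether days of temporary withdrawal count in it. Reasons for reduction show that a reduction happened, but carry no date. Together the three items give the number who ever reached the top step and why some left it. They do not say how long it was held.

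The adverse event table does not supply this. An event in week 1 at one eighth of the ceiling and an event in month 5 at the full dose count alike, unless the event itself led to a dose change. At stake is whether a reader can tell a dose that most patients sustained from one that many reached only briefly.

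**Working it through.** The plan states no figure for time at dose, so there is none to reproduce. The calculation uses the plan's schedule.

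**Inputs from the protocol synopsis.** Titration takes 3 × 7 = 21 days. Treatment lasts 6 months. Safety visits fall at months 1 (+/- 2 days), 2, 4 and 6 (+/- 7 days each). Adult steps are 25, 50, 100 and then 200 mg/day. Pediatric steps are 0.5, 1, 2 and then 4 mg/kg/day. Both run 12.5%, 25%, 50% and 100% of the ceiling, so the percentages below apply to both. Enrolment is up to 50.

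**Assumptions.** One month is 30.44 days, so 6 months is 182.6 days. Titration is completed on schedule, step-down is by one level at a visit, there is no later re-escalation, and only the core phase is counted.

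**Days at the top step (T)** = day of step-down, or end of treatment, minus 21.

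**Mean adult dose** = [7×25 + 7×50 + 7×100 + 200×T + 100×(161.6 − T)] / 182.6 mg/day, divided by 200 for the share of the ceiling. The titration terms sum to 1,225 mg.

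| Course | T (days) | Mean dose (mg/day) | % of ceiling |
|---|---|---|---|
| Step-down at month 1 | 30.4 − 21 = 9.4 | 100.4 | 50.2 |
| Step-down at month 2 | 60.9 − 21 = 39.9 | 117.0 | 58.5 |
| Step-down at month 4 | 121.8 − 21 = 100.8 | 150.4 | 75.2 |
| No step-down | 182.6 − 21 = 161.6 | 183.7 | 91.9 |

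All four have the same maximum dose and a duration of about 183 days. The first three also show a reduction with a reason, but nothing separates them from one another.

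**Visit windows.** The month 1 case has +/- 2 days at week 3 and +/- 2 at the visit: 9.4 +/- 4, or 5.4 to 13.4 days. The others have +/- 2 and +/- 7: 39.9 +/- 9 is 30.9 to 48.9; 100.8 +/- 9 is 91.8 to 109.8; 161.6 +/- 9 is 152.6 to 170.6. The ranges do not overlap.

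**Whole cohort.** If 50 patients complete 6 months, exposure is 50 × 6 = 300 person-months. Titration takes 50 × 21 / 30.44 = 34.5 (11.5%), leaving at most 300 − 34.5 = 265.5 at the ceiling. Each patient who steps down at month 1 loses (161.6 − 9.4) / 30.44 = 5.0 months there. If 10%, 30% or 50% did so, 240.5, 190.5 or 140.5 person-months would remain. These shares are assumed; the plan gives none.

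**Precision of a direct measure.** Exact (Clopper-Pearson) 95% intervals for keeping the top step to month 6 among 50 enrolled, with illustrative counts: 45/50, 78.2 to 96.7%; 35/50, 55.4 to 82.1%; 25/50, 35.5 to 64.5%.

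**The case against.** The strongest reply has four parts.

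1. *Reduced patients are already visible.* A reader might infer that a patient with 9 days at the top step looks exactly like one with 162. The plan does not support that, because reasons for reduction are reported and only the first patient has one. What stands is narrower: early and late reductions cannot be told apart.
2. *Dose-limiting events are already tied to dose.* A reader might infer that no adverse event can be placed at the top dose. For diarrhea or weakness that caused a step-down, it can: if the maximum dose was the top step and there was a single reduction, the event occurred on that step. The gap is confined to events that did not change the dose.
3. *The primary endpoint covers drug up to the ceiling, not drug at the ceiling.* A reader might infer that the adverse event percentages are wrong or diluted. For the titrated regimen in the endpoint they are valid. A patient whose diarrhea or weakness led to step-down is already counted as affected, so shorter time at the top dose does not dilute those events. It matters only against the aim in Study methodology.
4. *Treatment status is not empty just because everyone receives drug.* Temporary withdrawal, and monitoring for 30 days after discontinuation, create off-drug time. A definition would settle the term; its absence alone would be only missing detail.

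It is also fair to say that the scenarios are illustrations, and that the added tables could be made later from the same data if the dates are recorded. All of this limits the point. None of it shows how long the top dose was held.

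**Conclusion.** The concern holds in a limited form. The three planned tolerability items do not measure how long the maximal dose was sustained, although that is the aim in Study methodology. Among patients who reach the top step, stay on drug to month 6 and step down once at the month 1, 2 or 4 visit, time at that step runs from about 9 to about 101 days with identical maximum dose and duration. It is about 162 days with no step-down. Adverse events that led to no dose change have no stated link to the dose at onset.

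The figures rest on titration on schedule, step-down at a visit by one level and no re-escalation. How many patients will step down is unknown, so the effect on the final report cannot be sized in advance. The main adverse event table stands. This is a change worth considering in a small descriptive trial, not a flaw that invalidates its primary analysis.

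**What to change.** Amend Statistical Methodology as follows, before the data are seen.

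1. **Exposure.** Report the date of each reduction and temporary withdrawal, days at each dose level with withdrawal days counted separately, and mean daily dose as a percentage of the ceiling (100 mg b.i.d. for adults; 2 mg/kg b.i.d. on the dosing weight for children).
2. **Sustained top dose.** Report the number and percentage of all enrolled patients who reached the top step and kept it to month 6, with an exact 95% interval. Drop-outs count as not kept, even if replaced. Split the reasons into intolerance, physician choice and other. Repeat descriptively at months 12, 18 and 24 for extension participants.
3. **Supportive table by dose.** Define treatment status by the last dose level actually taken before onset, in four classes: before first dose, on drug below the ceiling, on drug at the ceiling, and off drug (temporary withdrawal or after the last dose). Assign by dose time, not calendar day, so that an event after the first dose at a new level counts at that level. This matters because an ECG is planned 4 hours after the very first dose. Laboratory events are dated when detected, so for these also show the dose level since the previous test. Give patients affected and person-months in each class. Put no Poisson limits on event counts, since events such as diarrhea can recur in one patient.
4. **Main table.** Keep the table in all enrolled patients as the main adverse event table.

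The cost is a few descriptive tables, with no added patients, visits or tests. They depend on dose-change and adverse event onset dates, and the times on days of dose change, being recorded. Cells in the by-dose table will be small, and patients who step down are a selected group, so that table should be labelled supportive.
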